Subjects will be treated for 16 weeks with study drug. Approximately 533 subjects will be enrolled in each treatment group for a total enrollment of approximately 1066 subjects.

Baseline Visit

At the Baseline visit, a review of any changes to the subject's medical (including cardiac) condition or current medications/other therapies will be performed. Subjects will then undergo clinical evaluation, including a targeted physical exam. This should include measurements of weight and vital signs, including orthostatic blood pressure, and an exam of the lungs, heart, oral cavity, and skin. The Clinical Frailty Scale (see [Section 13.4](#) [Appendix 4]) score of each subject will also be determined. An ECG will be performed for Baseline safety assessment. Subjects will also have blood and urine samples obtained for Baseline safety assessments. In addition, blood samples will be obtained for biomarker analyses, including RNA expression and soluble biomarkers. Consent for Optional Blood Storage for Future Use and Consent for Optional Pharmacogenetic Analysis will be obtained at the Baseline Visit. A single blood sample will also be obtained at the Baseline Visit in those subjects who sign the option Pharmacogenetic Analysis consent form for the purposes of possible future Pharmacogenomic analysis. A mid-turbinate nasal swab specimen will be collected.

Prior to randomization, the inclusion and exclusion criteria will be reviewed again, and eligible subjects will be randomized via the IXRS system to 1 of 2 treatment groups in a ratio of 1:1.

- RTB101 10 mg once daily (QD)
- Matching placebo QD

Randomization will be stratified based on the following factors that may influence the incidence or severity of clinically symptomatic respiratory illness and/or the response to RTB101 treatment:

1. Age \geq 85

2. Age ≥ 65 and < 85 years with a medical history of asthma
3. Clinical Frailty Scale score ≥ 4

Subjects will be given their first dose of study drug (and time of dosing recorded in the eDiary) at the study site and trained on use of the eDiary containing study assessments to be completed at home including:

- Study drug dosing information, to be completed daily through the Week 16 study visit
- Respiratory Illness Symptom Questionnaire, to be completed daily in the evening through the Week 20 study visit
- EQ-5D-5L, to be completed each day subjects report experiencing one or more respiratory illness symptoms through the Week 16 study visit

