¹¹ All subjects will be administered their first dose of study drug at the site at the Baseline Visit. Approximately 400 subjects (per IXRS randomization) will be required to undergo PK assessment in the study (~ 200 from each treatment arm). For subjects participating in the PK analysis for the study, at the Week 4 (or Week 6 if applicable) and Week 12 study visits, study drug should not be taken at home and instead study drug will be administered together with a light meal at the study site following the pre-dose PK draw. If PK sampling cannot be performed at the Week 4 visit for logistical reasons, it should be collected at the Week 6 visit instead, but according to the schedule described above for Week 4. This applies to timing of biomarker samples originally scheduled for Week 4 as well.

^{12a} Subject will be given a personal tablet device containing the eDiary and instructions on use at this visit.

^{12b} The personal tablet device containing the eDiary will be collected from the subject at this visit.

¹³ Health Related Quality of Life (EQ-5D-5L) to be completed by all subjects at Baseline and Week 16, and each day that they report experiencing one or more respiratory illness symptoms through Week 20.

¹⁴ Nasopharyngeal swabs for respiratory pathogen PCR is to be done during a scheduled or an unscheduled visit for all subjects who report at least one unique respiratory symptom (runny nose, sneezing, stuffy nose, sore throat, hoarseness, or cough) on 2 consecutive entries in their eDiary. The swabs should be obtained if they are able to within 48 hours of 2 consecutive eDiary entries of one or more unique respiratory symptoms. Subjects who record at least 1 respiratory symptom and at least 1 general (headache, feverishness/chills or loss of appetite) symptom, both of which are moderate or severe on two consecutive days in their eDiary, should be brought in within 24 hours of the second day of eDiary symptom entry. Subjects who are unable to come to the study site may also have the nasopharyngeal swab (and, if indicated, a sputum specimen and RIDT) obtained during a home visit by trained personnel. Only one nasopharyngeal swab should be obtained during each episode of respiratory illness. Nasopharyngeal swabs will be collected through Week 20, see the SOM for more details.

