6.7. Efficacy

6.7.1. Clinically Symptomatic Respiratory Illnesses

Respiratory illness symptoms will be captured in an eDiary that subjects will complete daily (in the evening) at home after the Baseline visit. The eDiary will ask the subject to record whether a predefined set of respiratory illness symptoms have occurred during the past 24 hours that are new or reflect a change from normal baseline symptoms. The predefined symptoms include both respiratory symptoms (runny nose, sneezing, stuffy nose, sore throat, hoarseness, or cough) and general symptoms (headache, feverishness/chills, loss of appetite, body aches, or lack of energy).

A clinically symptomatic respiratory illness will be defined programmatically as the occurrence of 2 respiratory symptoms (runny nose/sneezing (programmatically considered one symptom), stuffy nose, sore throat, hoarseness, or cough) or 1 respiratory and 1 of the following general symptoms (headache, feverishness/chills or loss of appetite), with at least 1 unique respiratory symptom (runny nose, sneezing, stuffy nose, sore throat, hoarseness or cough) being reported on 2 or more consecutive entries in an eDiary, and at least 2 symptoms being at least moderate in severity. Subjects who have clinically symptomatic respiratory illness may include subjects with a common cold, bronchitis, influenza-like illness, or pneumonia.

Further details will be provided in the Statistical Analysis Plan (SAP).

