7.2. Key Definitions

7.2.1. Clinically Symptomatic Respiratory Illness (CSRI)

A CSRI is defined as the occurrence of:

- a. At least 2 respiratory symptoms (runny nose/sneezing [considered one symptom], stuffy nose, sore throat, hoarseness, or cough) OR 1 respiratory symptom and 1 of the following general symptoms (headache, feverishness/chills or loss of appetite),

AND

- b. at least 1 of these respiratory symptoms (runny nose, sneezing, stuffy nose, sore throat, hoarseness or cough) in (a) above being reported on 2 or more “consecutive entries” in the eDiary, and must
 - i. overlap with another respiratory or general symptom for at least 1 day, or
 - ii. be reported on a consecutive day to another respiratory or general symptom in the eDiary

AND

- c. any 2 or more symptoms (respiratory and/or general) reported during the CSRI event that are at least moderate in severity.

All CSRI-defining symptoms (i.e., runny nose, sneezing, stuffy nose, sore throat, hoarseness, cough, headache, feverishness/chills or loss of appetite) that occur after the start of a CSRI event will be included as part of a single CSRI event unless there is a period of ≥ 7 consecutive entries during which all CSRI-defining symptoms are reported as “Absent” in the eDiary.

“consecutive entries” include situations in which eDiary entries were missing for 1-6 days in between 2 days in which the symptom was reported. For example, if on Day 3 and Day 9 runny nose was reported but eDiary entries were missing from Days 4-8, then runny nose will be considered as reported for 2 consecutive entries. This definition of “consecutive entries” does not include situations in which subjects report all symptoms as “Absent”. If ≥ 7 days of eDiary entries are missing, then symptoms reported before and after the ≥ 7 days of missing entries will not be considered consecutive eDiary entries.

The start date of the CSRI will be the start date of the first respiratory symptom reported as part of the CSRI. Note that the start date of a CSRI will always be based on the start date of the respiratory symptom and not a general symptom.

This document is confidential.

The end date of the CSRI will be defined as the latest date that any of the CSRI-defining symptoms for the same CSRI event were reported.

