9.4. Analyses of Secondary Efficacy Endpoints

9.4.1. Percentage of Subjects with One or More Clinically Symptomatic Respiratory Illnesses Associated with ≥ 1 Laboratory-confirmed Pathogen(s)

The percentage of subjects with CSRI associated with ≥ 1 laboratory-confirmed pathogen(s) beginning at least 3 days after the start of study drug treatment through Week 16 (H_2) as assessed by pre-specified clinical diagnostic criteria and respiratory pathogen PCR of nasopharyngeal swabs, sputum gram stain and culture, and/or RIDTs will be analyzed in the same manner as the primary efficacy analysis as described in 9.3.1 based on the estimand for the secondary objective corresponding to this endpoint described in 9.2.2 above.

Laboratory results from a specimen obtained within 3 days before the CSRI start date through the CSRI end date will be used to determine if the CSRI is associated with ≥ 1 laboratory-confirmed pathogen. Laboratory confirmation includes a positive respiratory pathogen PCR of nasopharyngeal swabs, sputum gram stain and culture, and/or RIDT. If multiple specimens are obtained for a particular CSRI, then any positive result will be counted as laboratory confirmation if it occurs within 3 days before the CSRI start date through the CSRI end date. A laboratory-confirmed CSRI may be associated with multiple pathogens. Note that organisms considered to identify a positive sputum specimen should meet standard microbiological laboratory criteria of growing from a sputum specimen with > 25 WBC/hpf and < 10 Squamous cells/ hpf, and they have matching morphology on gram stain and culture.

Summary statistics will be presented along with a full data listing by treatment group.

9.4.2. Rate of Clinically Symptomatic Respiratory Illnesses (with or without an Associated Laboratory-confirmed Pathogen)

The rate of CSRI (with or without an associated laboratory-confirmed pathogen) beginning at least 3 days after the start of study drug treatment through Week 16 (H_3) will be analyzed based on the negative binomial distribution. The first 3 days of study drug treatment will not be included in determining the denominator of rate.

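### The laboratory-confirmation window for H2 and H4 closes on the last symptom day, so some swabs taken on the protocol's own schedule fall outside it and short CSRIs count as unconfirmed

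*SAP*

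**What the plan says.** **Window.** SAP 9.4.1 (H2) uses "Laboratory results from a specimen obtained within 3 days before the CSRI start date through the CSRI end date", and where there are several specimens "any positive result will be counted as laboratory confirmation if it occurs within 3 days before the CSRI start date through the CSRI end date". SAP 9.4.3 (H4) refers back to this rule. The mid-turbinate analyses in SAP 9.6.1 and 9.6.2 use the same dates.

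**End date.** SAP 7.2.1 has the CSRI end date "defined as the latest date that any of the CSRI-defining symptoms for the same CSRI event were reported", at any severity. Later symptoms belong to the same event "unless there is a period of ≥ 7 consecutive entries during which all CSRI-defining symptoms are reported as" Absent.

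**Shortest event.** Protocol 6.7.1 requires at least one respiratory symptom "being reported on 2 or more consecutive entries in an eDiary", so two entries are enough.

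**Swab timing.** Protocol 3.1 sets the diary as "Respiratory Illness Symptom Questionnaire, to be completed daily in the evening through the Week 20 study visit". Protocol Table 6-1, footnote 14, says "The swabs should be obtained if they are able to within 48 hours of 2 consecutive eDiary entries" of a respiratory symptom. It calls for a visit within 24 hours when a respiratory and a general symptom are both moderate or severe on two days, and it limits subjects to one nasopharyngeal swab per episode. Under Protocol 3.1, a subject who is symptomatic at a scheduled visit may be swabbed there.

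**Testing order.** Under SAP 9.1, H2 is tested only if H1 is significant, and H4 only if H1 to H3 are.

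**The concern.** The protocol aims for a swab within 48 hours of symptom confirmation because viral detection is best then (Protocol 3.2 and 6.7.4). The SAP can discard exactly that specimen if the illness has already ended. The H2 and H4 estimands in SAP 9.2.2 deal with study discontinuation and missing diary data. They have no rule for a CSRI without an in-window specimen, so such a CSRI scores the same as one with a negative swab.

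Two things are at stake. First, H2 follows H1 in the sequence and its failure stops H3 to H9, so lost confirmed events cost power where the chain is most exposed. Second, the loss depends on how long the illness lasts. Protocol 3.2 names symptom duration among the things the secondary endpoints are meant to test. If duration differs by arm, the chance that a true infection is confirmed differs by arm too.

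**Working it through.** **1. Timeline (documents only).** Day 1 is the first respiratory symptom.

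- Second consecutive entry: evening of day 2.
- On-time swab: normally day 3 or 4 (day 3 on the 24-hour route).
- 2-day CSRI: the window closes on day 2, so the triggered swab is normally too late.
- 3-day CSRI: counted if swabbed on day 3, lost if swabbed on day 4.
- Longer CSRI: covered if the two-entry run comes at the start and 48 hours is met.

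**2. The plan's own figure.** SAP 3.6 gives 28.2% v 19.7%, 1066 subjects (533 per arm), two-sided 0.05, likelihood-ratio chi-square, 90% power. The noncentral chi-square calculation gives 0.903, so the figure reproduces. No power is stated for H2 or H4.

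**3. Share missed (assumed durations).** Take duration as 2 days plus a geometric tail, with the swab equally likely on day 3 or 4. For mean m, let q = (m − 2)/(m − 1). Then P(duration ≥ 3) = q, P(duration ≥ 4) = q², and the in-window share is (q + q²)/2.

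| Mean (days) | q | In window | Missed |
|---|---|---|---|
| 10 | 8/9 | (0.889 + 0.790)/2 = 0.840 | 16% |
| 7 | 5/6 | (0.833 + 0.694)/2 = 0.764 | 24% |
| 6 | 4/5 | (0.800 + 0.640)/2 = 0.720 | 28% |

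The geometric shape is unfavourable to the plan because its most common value is the 2-day minimum. Across geometric, gamma and lognormal shapes with placebo means of 6 to 12 days, the missed share runs from 0.4% to 28%.

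**4. Power if the loss is equal in both arms.** Assume 55% of CSRIs are confirmable: 0.282 × 0.55 = 15.5% v 0.197 × 0.55 = 10.8%, giving H2 power of 62%. Lose 20% of these in each arm (× 0.80): 12.4% v 8.7%, power 51%.

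**5. Bias if illness is also shortened.** The H2 ratio is multiplied by the ratio of in-window shares. For 7 to 5 days, geometric: the share at mean 5 is (0.750 + 0.5625)/2 = 0.656, and 0.656/0.764 = 0.86. For 10 to 8 days: the share at mean 8 is (0.857 + 0.735)/2 = 0.796, and 0.796/0.840 = 0.95.

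- No effect on incidence: expected H2 ratio 0.86 to 0.89 (7 to 5 days) and 0.95 to 0.98 (10 to 8 days) over the three shapes. All settings together give 0.77 to 0.995, or 0.66 to 0.98 if a quarter of swabs slip to day 6.
- True prevention as planned (19.7/28.2 = 0.70) plus 7 to 5 days: 0.70 × 0.86 = 0.60, and 0.62 with the gamma shape. With every triggered swab counted, the ratio is 0.70.

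Steps 4 and 5 are alternatives and do not add. In the prevention-plus-shortening case (geometric, 7 to 5 days, 50% positive), simulated nominal H2 power is 71% under the current window and 57% with all swabs counted. The extra power is bias.

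**6. The gate.** With shortening only, H1 is null and is favourably significant 2.5% of the time. In 200,000 simulated trials per setting (7 to 5 and 10 to 8 days, two shapes, 50% or 70% positivity), H1 and H2 both succeed in 0.9% to 2.0% of trials. The figure is 0.7% to 1.1% when every swab counts. H4 was not simulated; the same per-event loss applies.

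**The case against.** A reader might infer that a drug which merely shortens illness would be declared effective on H2 and H4. The documents do not support that. CSRI incidence would be unchanged, the sequence would normally stop at H1, and step 6 shows a formal H2 success to be rare. Nominal favourable significance on H2 is more common (11% to 17% for 7 to 5 days, 3% to 6% for 10 to 8 days, against 2.5%), but the plan would make no claim on it.

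A reader might also infer that short CSRIs are always unconfirmed. That is too strong as well. A scheduled visit can supply a swab, the 24-hour route favours day 3, and one mild CSRI-defining symptom within the next few days moves the end date past the swab. H2 is per subject, so a later confirmed CSRI still counts.

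H5 is not direct evidence that the window shortens. Its clock stops when symptoms are absent or mild (SAP 9.4.4), whereas the window runs until no CSRI-defining symptom is reported. RTB101 could improve H5 and leave the end date unchanged.

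Tying specimens to symptomatic days is defensible in itself. SAP 9.5.1 also counts viral positives whether or not they belong to a CSRI, and the planned listings would allow a check afterwards.

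All of this limits the size. The mismatch remains: the endpoint in SAP 9.5.1 is exploratory and does not replace H2 or H4, a listing is not a pre-specified analysis, and the analyses in SAP 9.6 keep the same window.

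**Conclusion.** The point holds as a mismatch between the SAP's window and the protocol's swab schedule. Most 2-day CSRIs and some 3-day CSRIs lose a compliant specimen and are scored unconfirmed, and no planned analysis tests that choice. The direction is clear: fewer confirmed events for H2 and H4 and, if RTB101 shortens total illness, estimates tilted in its favour.

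The size cannot be settled from the documents. It rests on assumed durations, positivity (50% to 70%) and swab days. With mean durations of 6 to 12 days it ranges from negligible (0.4% of placebo CSRIs) to material (28%). The realistic harm is either reduced H2 power (62% to 51% in the worked case) or an exaggerated estimate once H1 has succeeded (0.60 to 0.62 in place of 0.70 in the 7-to-5-day case).

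**What to change.** In SAP 9.4.1, and in parallel in 9.6.1, close the window after the protocol's swab schedule has run. For example: a specimen counts if obtained from 3 days before the CSRI start date through 3 days after the CSRI end date. The triggering second entry falls on or before the end date, so a 48-hour swab falls by about end date + 2 and the third day is a margin. Windows of successive CSRIs cannot overlap. SAP 7.2.1 requires at least 7 Absent days before a new event, so the next one starts no earlier than end + 8 and its window opens no earlier than end + 5.

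If the primary rule is kept, pre-specify the extended window as an H2/H4 sensitivity analysis. In either case, report by arm the number of CSRIs with no in-window specimen and the number with a specimen only after the end date. Because 48 hours is a target and not a limit, that table also shows how much late swabbing remains. Multiple imputation of confirmation status is optional.

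The cost is SAP wording, one analysis and one table, all from data already collected, and it should be settled before unblinding. The downside is that an unrelated pathogen may occasionally be counted.

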3.4. Brief Description

This is a randomized, double-blind, placebo-controlled, multicenter, parallel-group, Phase 3 study to determine if RTB101 prevents clinically symptomatic respiratory illnesses (CSRI) in elderly subjects. Approximately 1066 subjects will be enrolled during cold and flu season. Subjects who meet the inclusion/exclusion criteria will be randomized 1:1 to receive RTB101 10 mg or matching placebo orally

This document is confidential.

once daily for 16 weeks. The study will be composed of: up to a 4-week screening period, a 16-week treatment period, and a 4-week short-term follow-up period off study drug through the Week 20 Visit. There will also be a long term follow-up by telephone at Week 48.

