A separate CSRI event will not be diagnosed until a subject has ≥ 7 consecutive days during which all CSRI-defining symptoms are reported as “Absent” after the end date of the prior CSRI episode. If missing days of eDiary entries are sandwiched between 2 days of eDiary entries during which all CSRI-defining symptoms are reported as “Absent”, then all symptoms will also be considered as “Absent” for the missing eDiary entries, and a separate CSRI event can be diagnosed if the ≥ 7 consecutive days criterion is met. For example, if on Day 4 and Day 10 all symptoms were reported as “Absent” in the eDiary, and on Days 5-9 the eDiary entries were missing, then all symptoms will be considered as “Absent” on Days 5-9. Therefore all symptoms will be considered as “Absent” for 7 consecutive days (Days 4-10), and a separate CSRI can be diagnosed.

Only CSRI events having a start date at least 3 days after the start of study drug and meet the definition of a CSRI by the specified time point (Week 16 or Week 20) will be included in the analysis. Only data recorded in the eDiary through the evening before the Week 16 visit will be included in all analyses of CSRI events for the Week 16 endpoint. Similarly, only data recorded in the eDiary through the evening before the Week 20 visit will be included in all analyses of CSRI events for the Week 20 endpoint.

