9.2.2. Secondary Objective Estimands

1. The estimand for the secondary objective “To determine if RTB101 as compared to placebo decreases the percentage of subjects with a CSRI associated with ≥ 1 laboratory-confirmed pathogen(s) through Week 16” is defined by the following:

- Population:
 - Subjects in FAS population
- Variable:
 - Occurrence of a CSRI with ≥ 1 laboratory-confirmed pathogen(s) by the Week 16 visit

This document is confidential.

- Intercurrent events:
 - If a subject discontinues study prematurely due to an RTI AE or RTI SAE and the subject did not meet the definition of a CSRI associated with ≥ 1 laboratory-confirmed pathogen(s), assume the subject experienced a CSRI with ≥ 1 laboratory-confirmed pathogen(s)
 - If a subject discontinues study prematurely for any reason other than an RTI AE or RTI SAE, and the subject did not meet the definition of a CSRI associated with ≥ 1 laboratory-confirmed pathogen(s), impute the subject did not have a CSRI with ≥ 1 laboratory-confirmed pathogen(s)
 - If a subject completed the study and has intermittent missing eDiary data and the subject did not meet the definition of a CSRI associated with ≥ 1 laboratory-confirmed pathogen(s), impute the subject did not have a CSRI with ≥ 1 laboratory-confirmed pathogen(s)
 - Population-level summary:
 - odds ratio, i.e. the ratio of the odds of having a CSRI with ≥ 1 laboratory-confirmed pathogen(s) in subjects treated with RTB101 compared to the odds of having a CSRI with ≥ 1 laboratory-confirmed pathogen(s) in subjects treated with placebo by the Week 16 visit
2. The estimand for the secondary objective “To determine if RTB101 as compared to placebo decreases the rate of CSRIs, with or without an associated laboratory-confirmed pathogen, through Week 16” is defined by the following:
- Population:
 - Subjects in FAS population
 - Variable:
 - Number of CSRIs with or without an associated laboratory-confirmed pathogen through the Week 16 visit
 - Intercurrent events:
 - If a subject discontinues study prematurely due to an RTI AE or RTI SAE and the subject did not meet the definition of a CSRI, assume the subject experienced one CSRI
 - If a subject discontinues study prematurely for any reason other than an RTI AE or RTI SAE and the subject did not meet the definition of a CSRI, impute the subject did not have a CSRI

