A generalized linear model analysis will be conducted using the number of CSRI per 16-week period (illnesses/16 weeks) as the dependent variable and will include treatment group, age (continuous covariate), Clinical Frailty Scale score (ordinal covariate), medical history of diabetes mellitus type 2 (Y/N), medical history of asthma (Y/N) medical history of CHF (Y/N), and receipt of current season influenza vaccination (Y/N) as fixed effects.

This document is confidential.

The rate ratio (RR) (RTB101 dose group to placebo) of the treatment effect will be derived from the model along with the 95% 2-sided confidence interval (CI). Model-adjusted mean rates for each treatment group and their corresponding 95% 2-sided CI will also be calculated.

The “log” link function will be used in the model and an offset term will be included to account for variable lengths of treatment exposure across the subjects. The unadjusted rate of CSRI per subject through Week 16 will be calculated by summing the number of total CSRIs per subject through Week 16 within each treatment group.

Analysis of this endpoint will be based on the estimand for the secondary objective corresponding to this endpoint described in 9.2.2 above.

Summary statistics will be presented along with a full data listing by treatment group.

9.4.3. Rate of Clinically Symptomatic Respiratory Illness Associated with ≥ 1 Laboratory-confirmed Pathogen(s)

The rate of CSRIs associated with ≥ 1 laboratory-confirmed pathogen(s) beginning at least 3 days after the start of study drug treatment through Week 16 (**H₄**) as assessed by pre-specified clinical diagnostic criteria and respiratory pathogen PCR of nasopharyngeal swabs, sputum gram stain and culture, and/or RIDTs will be analyzed in the same manner as described in 9.4.2 above, based on the estimand for the secondary objective corresponding to this endpoint described in 9.2.2 above. Section 9.4.1 describes which laboratory result will be used to determine if the CSRI is associated with ≥ 1 laboratory-confirmed pathogen.

Summary statistics will be presented along with a full data listing by treatment group.

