10.1. Extent of Exposure

Duration of exposure is defined as (Date of Last Dose – Date of First Dose) +1. If date of last dose is unknown then the date of last clinical visit no later than the Week 16 Visit will be used to impute the date of last dose. If there are temporary dose interruptions based on the data from the eCRF, then only the periods of time when study drug interruption did not occur will be used to calculate the duration of exposure. Duration of exposure will be summarized using descriptive statistics by treatment group. The duration of exposure (in days) will also be categorized as follows: <7, 7-<14, 14-<28, 28-<42, 42-<46, 56-<70, 70-<84, 84-<98, 98-<112, ≥112, and tabulated by treatment group..

A listing including study drug administration information from the eDiary will be presented.

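### The offset for the rate endpoints (SAP 9.4.2) is worded as treatment exposure, but events are counted through Week 16 whether or not the subject is still on drug; it should be observation time

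*SAP*

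**What the plan says.** SAP 9.4.2 fits a negative binomial model with a log link to H3. Its dependent variable is "the number of CSRI per 16-week period (illnesses/16 weeks) as the dependent variable", and "an offset term will be included to account for variable lengths of treatment exposure across the subjects". The section's only denominator rule concerns the start of follow-up: "The first 3 days of study drug treatment will not be included in determining the denominator of rate". It gives no formula and no end date for the offset.

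The same section bases the analysis on the matching estimand in SAP 9.2.2, whose variable is "Number of CSRIs with or without an associated laboratory-confirmed pathogen through the Week 16 visit". That estimand lists study discontinuation and missing eDiary data as intercurrent events. It does not list stopping study drug. SAP 7.2.1 sets the cut-off used at Week 16: "Only data recorded in the eDiary through the evening before the Week 16 visit will be included in all analyses of CSRI events".

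Protocol 5.4.2 and 5.5.2 keep subjects who stop drug in the study, including the daily eDiary, unless they withdraw consent.

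SAP 9.4.3 (H4), 9.5.2 (H7, all-cause hospitalisations) and 9.5.25 (H8, urinary tract infections) refer back to 9.4.2 for their model. SAP 9.2.2 has an estimand for H4 but none for H7 or H8.

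**The concern.** A rate needs a numerator and a denominator that cover the same person-time. If treatment exposure means time on drug, they do not. Take a subject who stops at Week 4, keeps up the eDiary and has one CSRI at Week 12. That subject contributes 1 event over 25 days (Day 4 to 28) instead of 1 event over 109 days (Day 4 to 112), a personal rate 109/25 = 4.4 times too high.

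For H3 and H4 this conflicts with the estimands in SAP 9.2.2. For H7 and H8 it conflicts only with the endpoint wording, which runs through Week 16.

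The error cancels between arms when stopping is equal and biases the ratio when it is not. It would matter because of the fixed sequence in SAP 9.1: H3 is tested only if H1 and H2 succeed, and a failed H3 closes H4 to H9.

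**Working it through.** **1. The plan's own figure.** Protocol 9.6 assumes 28.2% vs 19.7%, two-sided 0.05, 1:1 allocation, N = 1066 and 90% power. A likelihood ratio chi-square calculation gives 90.3% power at 1066 (N = 1056 for exactly 90%). The plan's figure is reproduced. The offset plays no part in it, and the documents state no power for H3, H4, H7 or H8.

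**2. Size of the bias on the literal reading.** With a drug-time denominator and all stoppers still observed, the ratio is multiplied by about

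mean placebo drug time / mean RTB101 drug time.

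If a fraction d stops at a time uniform over the 16 weeks, mean drug time is proportional to 1 - 0.5d. Stopping rates are assumptions.

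| RTB101 vs placebo stopping | Multiplier |
|---|---|
| equal | 1.00 |
| 10% vs 8% | 0.96/0.95 = 1.01 |
| 10% vs 5% | 0.975/0.95 = 1.03 |
| 15% vs 5% | 0.975/0.925 = 1.05 |
| 5% vs 15% | 0.925/0.975 = 0.95 |

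Allowing for the excluded first 3 days changes these by less than 0.01 (15% vs 5%: 1.056).

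**3. H3 event rates.** The proportions p are converted to mean counts by ((1-p)^(-k) - 1)/k, with dispersion k = 0.4 assumed:
- placebo: (0.718^(-0.4) - 1)/0.4 = 0.354
- RTB101: (0.803^(-0.4) - 1)/0.4 = 0.229
- ratio: 0.229/0.354 = 0.647

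**4. H3 power by simulation.** Set-up: 20,000 trials per scenario, 533 per arm, gamma-Poisson counts over 109 days, negative binomial fit with treatment only, two-sided 0.05. All stoppers stay observed, the drug effect is the same on and off drug, and drug time has a 1-day floor. With an observation-time offset, power is 94.6%.

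| Stopping, RTB101 vs placebo | Power, drug-time offset | Fitted ratio |
|---|---|---|
| 5% vs 5% | 94.6% | essentially unbiased |
| 15% vs 15% | 94.4% | essentially unbiased |
| 10% vs 8% | 93.5% | about 0.65 |
| 10% vs 5% | 91.5% | 0.67 |
| 15% vs 5% | 87.1% | 0.69 |
| 5% vs 15% | 98.0% | 0.61 |

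A separate run of 1,500 trials per scenario gave 93.0%, 86.3% and 98.2% for 10% vs 8%, 15% vs 5% and 5% vs 15%, against 94-95% with observation time.

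**5. Sensitivity at 15% vs 5%.**
- Dispersion from 0 to 1: power 84.8% to 89.3% with drug time.
- Half the stoppers leave the study: 90.9% (drug time) vs 94.3% (observation time).
- All stoppers leave: no difference between the offsets.
- Drug effect ends when drug stops: 77.8% (drug time) vs 90.5% (observation time).

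**6. Effect on the sequence.** If 60% of CSRIs are laboratory-confirmed (assumed), the share of trials that reach H3 and stop there is 0.2% with observation time. With drug time it is 0.4% at 10% vs 8% and 2.1% at 15% vs 5%.

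**The case against.** The strongest reply is that the text already points to the right denominator. The outcome is expressed per 16-week period and the estimand runs through Week 16. SAP 3.4 calls the same 16 weeks "a 16-week treatment period, and a 4-week short-term follow-up period off study drug through the Week 20 Visit", so treatment exposure may simply mean time in that period. The only drug-time formula is in SAP 10.1, where "only the periods of time when study drug interruption did not occur will be used to calculate the duration of exposure". That rule belongs to the safety section, and 9.4.2 does not cite it. All of this stands. A reader might infer that the SAP prescribes time on drug; the documents support only an ambiguity whose literal form conflicts with the estimand.

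Other stronger readings also fail:

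- **A large power loss.** Putting all stops in the first 4 weeks at 15% vs 5% takes power to 75.3%, but nothing in the documents suggests that pattern. The tolerability figures in Protocol 1.2.2 and 3.3 are mixed: Phase 2b diarrhea 4.5% vs 4.4% with no appreciable adverse event differences, and Phase 2a diarrhea 19% vs 8% over one year. None of these is a stopping rate.
- **Inflated study-wise error.** H1 and H2 use no offset and are tested first. With no drug effect and 5% vs 15% stopping, H1, H2 and H3 all favour RTB101 in 0.96% of trials with drug time and 0.75% with observation time.
- **An estimand conflict for H7 and H8.** SAP 9.2.2 has no estimand for either.
- **A clash between imputation and offset.** For a non-RTI dropout SAP 9.2.2 says "and the subject did not meet the definition of a CSRI, impute the subject did not have a CSRI". Such a subject already counts zero, so this does not by itself require a full 16-week denominator.
- **Contradictory diary-gap rules.** SAP 7.2.1 decides when a separate CSRI can be diagnosed; SAP 9.3.2.1 sets an adjustment for the tipping-point analysis of H1. They serve different purposes.

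**Conclusion.** The point holds as a wording fault that should be fixed. For H3 and H4, the literal offset conflicts with the estimands the SAP invokes. For H7 and H8 it conflicts with the endpoint wording only.

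The harm is conditional. It needs the literal reading, unequal stopping between arms, and stoppers who stay observed. It can go either way: more stopping on RTB101 pushes the ratio toward 1, and more stopping on placebo favours RTB101. A 2-point difference costs about 1 point of H3 power and a 10-point difference about 7 to 8 points, if the drug effect is the same on and off drug. These figures rest on assumed stopping rates, dispersion and event recurrence. Confidence is medium, because the intended meaning of the offset cannot be settled from the text.

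**What to change.** In SAP 9.4.2:

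1. Replace treatment exposure with the log of days under observation. The period runs from after the first 3 days to the earlier of the Week 16 cut-off and the last eDiary entry (last study contact for hospitalisations, urinary tract infections and other non-diary events), regardless of treatment status.
2. State that the dependent variable is the integer event count. With an offset in the model, a count per 16 weeks would adjust for time twice.
3. Make any drug-time rate supplementary, with its events limited to on-drug time.

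Rules for diary gaps, for dropouts with an imputed outcome, and for subjects with no time after Day 3 (whose log offset is undefined) can be written down at the same time. They are detail, not corrections of errors. The 16-week length could also be stated once: SAP 9.3.2.1 uses 111 days, which would make the full period 108 days rather than the 109 used here, with no material effect on the ratio.

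The cost is SAP wording and one derived variable from dates already collected. The sample size does not change.
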